8.4.1. Other Reasons for Discontinuation of Study or Investigational Product

The following events are considered appropriate reasons for a subject to discontinue investigational product; however, these subjects are expected to continue in the study until study termination (or at the discretion of the Sponsor):

- Subject begins treatment with commercially available OCA
- The Investigator or Sponsor considers that it is advisable or in the best interest of the subject.
- The occurrence of clinical or laboratory AEs considered by the Investigator to be clinically important safety concerns and related to study drug.
- Withdrawal of consent
 - Consent may be fully withdrawn (in which case the subject discontinues both investigational product and study visits and procedures).
 - Consent may be modified to discontinue study visits but allow semi-annual telephone contact.
 - Consent may be modified to discontinue study visits or semi-annual telephone contact but allow continued access to medical records to assess for suspected major adverse cardiovascular events (MACE) and liver-related clinical outcomes.
 - Early termination procedures should be conducted if the subject withdraws consent (See [Section 9.7.15](#)).

The Investigator is encouraged to contact the Sponsor prior to discontinuing a subject from treatment. The Investigator must notify the Sponsor study monitor by telephone or email as soon as possible if any subject prematurely withdraws from the study.

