13.1.2. Determination of Sample Size

The target population is subjects who are at higher risk of liver-related clinical complications. Eligible subjects will have a diagnosis of PBC with bilirubin levels $>ULN$ and $\leq 5x ULN$ and/or $ALP > 3 \times ULN$. The following assumptions were used in sample size calculations:

- Exponential survival curves, placebo survival estimate of 0.6 at 8 years with a hazard ratio of 0.60, and total study duration of 10 years (from first subject enrolled), allowing for 4 years of subject accrual and 6 years of follow up.
- Subjects will be randomized in a 1:1 ratio to placebo or OCA.
- The 2 groups will be compared using a 2-sided log rank test at the 5% level of significance.
- Two interim analyses and one final analysis are planned. The first interim analysis will be performed when 50% of the target events are accrued and the second interim will be performed when 75% of the target events are accrued.
- A dropout rate of 10% is assumed

Based on the randomization ratio, significance level, and assumed hazard ratio, a total of 127 events (both groups combined) will provide 80% power to demonstrate a statistically significant difference between OCA and placebo on time to liver-related outcomes, including all-cause mortality.

In addition, based on the remaining assumptions stated above, it is estimated that approximately 428 subjects will be enrolled to attain 127 events.

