13.1.9.1. Time to Event Endpoints

For the time to event analyses, subjects who do not experience an event will be censored at the time of their last contact. Subjects with no data after randomization will be considered to have an event on Day 1 (first day of investigational product dosing).

For analyses of the percentage of subjects with an event, subjects with no data after randomization will be considered to have an event.

All time to event endpoints include only adjudicated events. Sensitivity analyses may consider all events regardless of adjudication. Events with discrepant adjudication will be analyzed using both results.

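### Section 13.1.9.1 imputes a Day 1 event to subjects with no follow-up, against its own adjudicated-only rule; censoring at last contact is also loose for MELD ≥15

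*Protocol*

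**What the plan says.** Section 13.1.9.1 of the protocol sets three rules for time-to-event endpoints.

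- In general, "subjects who do not experience an event will be censored at the time of their last contact".
- As an exception, "Subjects with no data after randomization will be considered to have an event on Day 1". For analyses of the percentage with an event, these subjects again count as events.
- For all such endpoints, "All time to event endpoints include only adjudicated events". Sections 13.1.3 and 13.1.4 repeat this for the primary and key secondary analyses, and Section 13.4 requires committee review before an event enters any analysis.

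Section 13.1.9 assumes missing data are missing at random. Section 13.1.1 limits the ITT population to randomized subjects who received some product.

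On follow-up, Section 8.4.1 provides that "Consent may be modified to discontinue study visits but allow semi-annual telephone contact", or record review alone. Table 8 gives both groups a combined EOT/EOS visit and no scheduled visits afterwards. MELD is calculated from chemistry and coagulation values at visits (footnote p to Table 1). MELD ≥15 is a component of the primary endpoint and step 2 of the testing hierarchy (Section 13.1.10).

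**The concern.** The Day 1 rule creates an event that nobody observed and that has no source documents for a committee to review. It applies to all-cause death and transplant as well as to the composite. The analyst cannot obey both this rule and the adjudicated-only rule. The study runs to about 127 adjudicated events (Sections 7.1 and 7.8), so imputed events would enter the log-rank test without counting toward that target. Section 13.1.9 promises alternative imputation methods, and 13.1.9.2 and 13.1.9.3 supply them, but 13.1.9.1 offers no alternative to this rule.

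The censoring rule raises a lesser question. Read literally, last contact includes a telephone call. A subject followed only by telephone would then stay in the risk set for a laboratory-defined endpoint with no scheduled bilirubin, creatinine or INR. If one arm had more such time than the other, that arm would appear to have fewer MELD events.

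**Working it through.** **Inputs from Section 13.1.2.** "The 2 groups will be compared using a 2-sided log rank test at the 5% level of significance"; "a total of 127 events (both groups combined) will provide 80% power to demonstrate a statistically significant" difference; "placebo survival estimate of 0.6 at 8 years with a hazard ratio of 0.60"; "allowing for 4 years of subject accrual and 6 years of follow up"; 1:1 allocation; 10% dropout; 428 subjects. Section 13.1.12 adds looks at 64 and 96 events with Lan-DeMets O'Brien-Fleming boundaries.

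**The plan's own figures reproduce.**
- Freedman's formula gives (1.960 + 0.842)² × (1.6/0.4)² = 126 events, or 128 with an inflation of 1.020 for the interim looks. Schoenfeld's gives 121 and 123. The stated 127 agrees with Freedman.
- The final critical value is 2.016. Group-sequential power at 127 events is 79.7% (Freedman) to 81.3% (Schoenfeld).
- The placebo hazard is −ln(0.6)/8 = 0.0639 per year and the OCA hazard 0.0383. With uniform 4-year accrual and 10 years in total, the event probabilities are 0.398 and 0.263, mean 0.331. Then 127/0.331 = 384, and 384/0.9 = 427, against 428 stated.

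**Day 1 rule, by log-rank score.** Without imputation U = −ln(0.6) × 127/4 = 16.22 and V = 127/4 = 31.75. At Day 1 the risk sets are about equal, so each imputed OCA event changes U by −0.5, each placebo event by +0.5, and either adds 0.25 to V. HR = exp(−U/V), z = U/√V, and approximate power = Φ(z − 2.016).

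| Imputed OCA + placebo (assumed) | U | V | HR | z | Power |
|---|---|---|---|---|---|
| 0 + 0 | 16.22 | 31.75 | 0.600 | 2.88 | 81% |
| 1 + 0 | 15.72 | 32.00 | 0.612 | 2.78 | 78% |
| 3 + 0 | 14.72 | 32.50 | 0.636 | 2.58 | 71% |
| 5 + 0 | 13.72 | 33.00 | 0.660 | 2.39 | 65% |
| 1 + 1 | 16.22 | 32.25 | 0.605 | 2.86 | 80% |
| 4 + 4 | 16.22 | 33.75 | 0.618 | 2.79 | 78% |
| 0 + 4 | 18.22 | 32.75 | 0.573 | 3.18 | 88% |

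A simulation agrees. It used 214 per arm, no stratification, a stop at 10 calendar years and a critical value of 2.01. From a baseline HR of 0.595, 1 + 1 gives 0.602, 4 + 4 gives 0.618, 4 on OCA only gives 0.647 and 4 on placebo only gives 0.573. With a true HR of 1, rejection in favor of OCA rises from about 2.2% to 4.5% with 4 imputed on placebo only. Balanced imputation does not inflate it.

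**Last-contact rule, by simulation.** The documents give no telephone-only share and no MELD share. Assumed: 10–30% of an arm, starting at a uniform time in years 0–6; no MELD detection afterwards; MELD 30–60% of primary events; true HR 0.60.

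| Telephone-only, OCA vs placebo | HR, composite | HR, MELD ≥15 |
|---|---|---|
| Equal (10% or 20% in both) | 0.598–0.602 | 0.59–0.60 |
| 20% vs 10% | 0.577–0.588 | 0.551–0.555 |
| 30% vs 10% | 0.560–0.577 | 0.513–0.517 |
| 10% vs 20% | 0.609–0.620 | 0.638–0.640 |

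With 30% vs 10% and a true HR of 1, rejection in favor of OCA is 3–5% for the composite and 6–11% for MELD ≥15. Censoring at the last laboratory-evaluable visit returns the HR to 0.59–0.60 in every scenario tried, for both endpoints.

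**The case against.** The Day 1 rule can reach very few subjects. ITT membership requires a dose, and the first dose is taken the day after the Day 0 visit (Section 9.1), so most proof of dosing is itself data after randomization. One subject per arm moves the HR by less than 0.01. This stands and limits the size, but it does not remove the contradiction.

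A reader might infer that OCA subjects lost to pruritus would be turned into events. The documents do not support that. A subject who reports pruritus and stops product has an adverse event record and a discontinuation reason, so the rule does not apply and the subject is censored at last contact. Nothing ties subjects who vanish without any report to one arm.

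A reader might also infer that stopping product moves a subject to telephone follow-up. It does not. Sections 7.6, 8.4 and 9.2.1 expect discontinuers, including those starting commercial OCA, to keep the regular visits; telephone follow-up needs a separate change of consent. Table 8 footnote c allows hepatic outcome data to be collected at these contacts, so death, transplant and hospitalization can still be found and MELD detection need not be zero. The protocol never says that telephone time is MELD-event-free; that follows only from a literal reading of last contact, which the SAP may narrow. All of this stands, so the second point is conditional.

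**Conclusion.** The Day 1 rule should be fixed. It cannot be reconciled with the adjudicated-only requirement, and under the protocol's missing-at-random assumption these subjects would be censored. Its likely effect is small: an HR of 0.60 becomes about 0.605 with one subject per arm, and 0.61–0.66 with one to five on OCA only. Those counts are assumptions. The direction depends on where the subjects fall: toward 1 if balanced, either way if not.

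The last-contact point holds only conditionally. Equal telephone-only shares lose MELD events but leave the HR undistorted; unequal shares bias it, in favor of the arm with more such follow-up. The stronger reading, that either rule biases the primary comparison whatever happens in the two arms, is not supported. Every size for this point rests on assumed shares and on no MELD detection during telephone follow-up.

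**What to change.** 1. In Section 13.1.9.1, censor subjects with no data after randomization at Day 1 in the primary analysis of every time-to-event endpoint. Keep the Day 1 event imputation as a named sensitivity analysis only.
2. For time to MELD ≥15, define the censoring date as the last laboratory date on which MELD could be evaluated.
3. For the composite, add a sensitivity analysis censored at the last visit with laboratory assessment.

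The cost is wording in the protocol or SAP and one or two extra runs, best settled before the first interim analysis. Some event-free follow-up would go unused. Censoring at the last laboratory date may itself be informative if sicker subjects stop attending, which is why it is proposed for the composite only as a sensitivity analysis.

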13.1.9.2. Quantitative Endpoints

For efficacy endpoints that utilize an ANCOVA model, observed cases will serve as the primary analysis. Sensitivity analyses to assess the effect of missing data may be conducted where missing data is imputed using last observation carried forward.

Sensitivity analyses of ANCOVA models will also be evaluated using a restricted maximum likelihood based mixed-effect repeated measures model where no imputations will be made for missing values.

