7.5.3. Clinical Criteria for Monitoring for Potential Hepatic Decompensation Events

Subjects will be monitored for potential hepatic decompensation events throughout the study. Clinical criteria for the monitoring these events and the interruption/discontinuation of investigational product is summarized in [Table 5](#).

Investigational product should be discontinued permanently if the subject received a liver transplant or experiences multi-organ failure as defined in Table 5, Part A). Subjects should continue to return for scheduled study visits for safety follow up.

Subjects who experience other potential hepatic decompensation events defined in Table 5, Part B should be closely monitored until normalization or stabilization. Subjects may be rechallenged after a minimum of 30 days if fully resolved OR stable and approved by the Medical Monitor and Investigator.

Table 5: Clinical Criteria for Monitoring Potential Hepatic Decompensation Events and Interruption / Discontinuation of Investigational Product

A. Hepatic Decompensation Events Requiring Mandatory Discontinuation of Investigational Product	
Decompensation Event	Action Taken / Rechallenging Criteria
Liver Transplant	Discontinue IP permanently and follow patients until normalization/stabilization.
Multi-organ failure requiring hospitalization:	Continue to return for scheduled study visits for safety follow up.
B. Hepatic Decompensation Events Requiring Interruption of Investigational Product	

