13.1.4. Key Secondary Efficacy Analyses

The key secondary efficacy endpoints will compare OCA to placebo on the following:

- Time to first occurrence of MELD score ≥ 15

- Time to liver transplant or death (all-cause)
- Change from Baseline in total bilirubin at end of study
- Change from Baseline in ALP at end of study

The key secondary efficacy analyses will compare OCA to placebo in the ITT population with respect to the key secondary efficacy endpoints. Only adjudicated events will be included in time-to-event analyses. The comparison (hypothesis testing) will be conducted as specified in [Section 13.1.10](#) in a sequential closed testing gate-keeping procedure, provided that the primary efficacy endpoint comparison is statistically significant in favor of the OCA treatment group. If the primary comparison is not statistically significant then comparison of the secondary endpoints will be considered as descriptive and exploratory. This procedure controls the study-wise type I error.

The 2 treatment groups will be compared using the same methodology as specified for the primary efficacy analysis ([Section 13.1.3](#)). The same analyses for key secondary efficacy endpoints will be performed for PP population as a sensitivity analysis.

Analyses of change from Baseline to end of study in ALP and total bilirubin will be compared between treatment groups using analysis of covariance (ANCOVA) with change from Baseline as the dependent variable including treatment group and randomization stratification factor as fixed effects and the Baseline values as a covariate. The same analysis will be carried out using percentage change from Baseline as the dependent variable.

Descriptive statistics of the laboratory values will be summarized by treatment group. The results, change from Baseline, and percentage change from Baseline values as well as estimates of least-square means, standard errors, and 95% CIs will be presented by treatment group. Estimates of the mean difference between treatment groups, the standard error of the difference, and 95% CI of the difference will be presented.

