13.1.9. Handling of Dropouts or Missing Data

Subjects who discontinue investigational product are expected to continue in the study until study termination.

Missing data will be assumed to be missing at random. In order to determine the effect of missing data on the analysis, efficacy endpoints will be analyzed using different methods of imputation as described below. In addition, the same analyses for primary and key secondary endpoints based on ITT and PP populations will be performed to assess robustness of analysis results. During the conduct of the study, the DMC may recommend refining the missing data strategy to better address the observed pattern of missing data, based on blinded monitoring of the data.

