13.1.10. Multiple Comparisons/Multiplicity

The key secondary efficacy endpoints are as follows:

- Time to MELD score ≥ 15
- Time to first occurrence of liver transplant or death (all-cause)
- Change from Baseline in total bilirubin at end of study
- Change from Baseline in ALP at end of study

The hypothesis testing of key secondary analyses will compare placebo and OCA and will be conducted in a sequential closed testing gate-keeping procedure (in the order in which the key secondary endpoints are stated above), provided that the primary efficacy endpoint comparison is statistically significant in favor of OCA. If the primary comparison is not statistically significant then comparison of the secondary endpoints will be considered as descriptive and exploratory.

This procedure controls the study-wise type I error.

- First (step 1) placebo and OCA will be compared with respect to the primary efficacy endpoint. If the comparison achieves statistical significance at 2-sided 0.05 level in favor of OCA group, then
- The time to MELD score ≥ 15 will be compared between placebo and OCA (step 2). If the comparison achieves statistical significance at 2-sided 0.05 level in favor of OCA group, then
- The time to liver transplant or death (all-cause) will be compared between placebo and OCA (step 3). If the comparison achieves statistical significance at 2-sided 0.05 level in favor of OCA group, then
- Change from Baseline in total bilirubin will be compared between placebo and OCA (step 4). If the comparison achieves statistical significance at 2-sided 0.05 level in favor of OCA group, then
- Change from Baseline in ALP at the end of study will be compared between placebo and OCA (step 5).

If at any step defined above the comparison is not statistically significant at the 2-sided 0.05 level then the remaining comparisons in the stated hierarchy will be considered descriptive and exploratory. The study-wise type I error will be maintained with the above closed procedure.

Additional efficacy endpoints will be analyzed; however, hypothesis tests will be applied for descriptive and exploratory purposes only.

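### The alpha-protected bilirubin and ALP tests use observed-case ANCOVA at a subject-specific end of study, which loses deaths, has no rule for post-transplant values, and probably understates a bilirubin benefit

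*Protocol*

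**What the plan says.** Section 13.1.4 lists as a key secondary endpoint "Change from Baseline in total bilirubin at end of study", followed by the matching change in ALP. On the method it states: "Analyses of change from Baseline to end of study in ALP and total bilirubin will be compared between treatment groups using analysis of covariance". The model contains treatment, the randomization stratification factor and the baseline value.

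Section 13.1.10 makes these two comparisons steps 4 and 5 of a fixed sequence. The earlier steps are the primary endpoint, MELD score of 15 or more, and transplant or death. Each step is tested at two-sided 0.05, and the section adds: "The study-wise type I error will be maintained with the above closed procedure".

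On missing values:
- Section 13.1.9: "Missing data will be assumed to be missing at random".
- Section 13.1.9.2, on the primary method: "For efficacy endpoints that utilize an ANCOVA model, observed cases will serve as the primary analysis".
- Section 13.1.9.2, on sensitivity: "Sensitivity analyses to assess the effect of missing data may be conducted where missing data is imputed using last observation carried forward". A REML mixed model for repeated measures without imputation is also committed to, again as sensitivity only.

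On timing, Section 9.7.1 defines end of study as the subject's final visit. Section 9.7.15 and Table 8 place it close to the last dose for a subject who leaves early. Section 7.1.3 expects at least about 6 years of follow-up in a study of about 10 years.

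On transplant, Section 7.5.3 stops study drug permanently and then states: "Subjects should continue to return for scheduled study visits for safety follow up". Chemistry is drawn at those visits (Table 2).

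**The concern.** A confirmatory laboratory comparison needs a defined time and a defined set of subjects. Here the time differs by subject, and the set is whoever still has a sample at that time. Those without a sample include everyone who died, and in this disease they are likely to be subjects whose bilirubin was rising. A transplanted subject can contribute a value from the new liver, which would read as improvement.

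The method also does not match the stated assumption. Under missing at random, loss may depend on bilirubin measured during the study. An observed-case ANCOVA that conditions only on treatment, baseline and strata is valid only if loss depends on nothing beyond those. The planned repeated-measures model uses the interim values, yet it ranks second.

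The stakes are specific. Steps 4 and 5 are confirmatory only if OCA has already won on transplant or death, which is the situation in which the arms lose different numbers of subjects. Step 4 also gates step 5, so a diluted bilirubin result would make ALP merely descriptive.

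**Working it through.** **1. The plan's own figures (Section 13.1.2).** Inputs: placebo event-free 0.6 at 8 years, hazard ratio 0.60, 4 years of accrual plus 6 of follow-up, 1:1 allocation, 80% power, two-sided 5%, 10% dropout.
- Hazards: placebo -ln(0.6)/8 = 0.0639 per year; OCA 0.6 x 0.0639 = 0.0383.
- Event probability with uniform accrual: 1 - [exp(-6λ) - exp(-10λ)]/(4λ).
- Placebo: 1 - (0.6817 - 0.5281)/0.2554 = 0.398. OCA: 1 - (0.7946 - 0.6817)/0.1532 = 0.263. Mean 0.331.
- Events: Freedman's formula gives 126, or 128.1 with the three-look inflation of 1.020, against 127 stated.
- Subjects: 127/0.331 = 384; 384/0.9 = 427, against 428 stated. The plan's figures reproduce.

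**2. Who necessarily lacks a value.** The 39.8% and 26.3% are first events of the whole composite, about 85 and 56 of 214 per arm without dropout. Section 7.6 keeps subjects with a non-fatal event on the visit schedule, so they can still supply an end-of-study sample. Deaths cannot. The protocol gives no split by component, so the share of event subjects who die before end of study is an assumption:

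| Share who die | Placebo without value | OCA without value |
|---|---|---|
| 10% | 4.0% (9) | 2.6% (6) |
| 25% | 10.0% (21) | 6.6% (14) |
| 40% | 15.9% (34) | 10.5% (23) |
| 60% | 23.9% (51) | 15.8% (34) |

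Counts are out of 214. The loss is unequal whenever OCA reduces deaths.

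**3. Direction, by illustration only.** The documents give no SD, slope or effect for bilirubin. An illustrative simulation assumed:
- baseline log-bilirubin SD 0.5, slope 0.08 per year (SD 0.12);
- a death/transplant hazard rising with current log-bilirubin (coefficient 0.5 to 1.5);
- 20-40% of those events being transplants, with bilirubin near 0.6 x ULN afterwards;
- end of study uniform over 6-10 years, with no early leavers.

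Results:
- OCA slope benefit of -0.05 per year, with or without a further direct effect on events (hazard ratio 0.7): observed-case ANCOVA recovers 52-90% of the difference that would be seen if all survived without transplant. In the most diluted case that is -0.205 against -0.398; dropping post-transplant values moves it to -0.295.
- OCA lowers events (hazard ratio 0.6) but not bilirubin: the estimate is +0.06 to +0.11 log units against OCA.
- 214 per arm, coefficient 1.0, 30% transplants, benefit of -0.03 per year: power 45%, against 70% with complete data.
- No effect on anything: rejection 1.5% + 2.7% = 4.2%, so no inflation.

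**4. How a fixed visit changes the loss.** Probability of any primary event by time t is 1 - exp(-λt). At 1 year: about 6% placebo and 4% OCA. At 6 years: 1 - 0.682 = 32% and 1 - 0.795 = 21%. The earlier the visit, the less the result depends on how death and transplant are handled.

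**The case against.** The strongest case against runs as follows. These are the last two gated laboratory endpoints, reached only after OCA has won on clinical outcomes. The likely error is conservative, so no false claim for OCA follows. The repeated-measures model is a firm commitment, Section 13.1.9 promises alternative methods and a per-protocol analysis, and the missing-data strategy may be refined on blinded review. Windows and post-transplant handling are often left to the SAP. A Month 12 contrast would ask a different, shorter-term question, and Study 747-301 already reported 12-month biochemistry. The repeated-measures model does not solve death either, because it extrapolates past it.

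Much of this stands. It lowers the consequence, rules out prescribing Month 12, and means the repeated-measures model needs a companion analysis that ranks death and transplant. It does not remove the point: the protocol itself fixes observed cases at end of study as primary, so this is not a detail left open for the SAP.

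A reader might infer that 40% and 26% of subjects are missing. The documents do not support that, since most non-fatal events leave the subject on the visit schedule. A reader might also infer that post-transplant values certainly enter the ANCOVA. The protocol neither includes nor excludes them; the visits continue for safety follow-up, and entry is only the default reading. Subjects who switch to commercial OCA also stay to the end (Section 9.2.1), so the direction of any bias is not settled by death and transplant alone.

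**Conclusion.** The point holds as a method weakness that should be changed. The protocol pairs a subject-specific time point with an analysis that ignores interim values, has no rule for death or transplant in these endpoints, and ranks below it a planned model that fits the stated assumption better. If OCA works, the probable result is an understated bilirubin benefit and lost power at step 4, which can also block step 5.

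The conclusion rests on bilirubin rising before death or transplant, and on fewer such events on OCA. The necessary loss is about 4-24% of placebo against 3-16% of OCA subjects over the assumed range of deaths. The amount of dilution cannot be derived from the documents; 52-90% recovery is an illustration on outside assumptions.

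Two stronger readings are tempting. One is that the procedure inflates type I error: nothing shows this, and the null simulation does not. The other is that ALP is biased in the same way: ALP shares the time point and the method, but no bias has been demonstrated for it.

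**What to change.** In Sections 13.1.4 and 13.1.9.2, with matching wording in the synopsis and in steps 4 and 5 of Section 13.1.10:

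- Make the already planned REML repeated-measures model over scheduled visits the primary analysis for both endpoints, with the contrast at one pre-specified visit that the sponsor chooses within the minimum follow-up. Month 12 is one option, not a requirement.
- Exclude laboratory values taken after liver transplant from these efficacy analyses.
- Keep observed-case end-of-study ANCOVA as a supportive analysis.
- Replace last observation carried forward with a worst-rank sensitivity analysis in which death or transplant ranks worst. This is needed because the repeated-measures model extrapolates past death and, once later values are excluded, past transplant.

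The cost is wording only, since chemistry is already drawn at the scheduled visits and the model is already planned. The downside is that the confirmatory statement will refer to a fixed visit and not to each subject's last value; an early visit reduces loss but gives up the long-term reading.
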